The stimulators used in this study for the CCFES and cNMES groups deliver biphasic rectangular current pulses at a pulse frequency of 35 Hz and pulse amplitude of 40 or 60mA. Up to 3 channels of stimulation will be used to produce hand opening. Surface electrodes will be positioned to activate the extensor digitorum communis (EDC) and extensor pollicis longus (EPL). Abductor pollicis brevis (AbPB), dorsal interossei (DI), or extensor indicis proprius (EIP) may also be targeted if they are necessary to achieve functional hand opening. A pulse amplitude (default, 40 mA) and maximum stimulus intensity (pulse duration) will be determined for each stimulus channel so as to achieve maximum finger and thumb extension without discomfort. For the CCFES group, each stimulus channel will be programmed so that stimulation intensities (pulse durations) change in proportion to the amount of opening of a CCFES glove worn on the unaffected hand. The CCFES glove is an assembly of bend sensors (Images SI, Inc., Staten Island, NY) attached to the fingers of an athletic batting glove. For the cNMES group, the stimulator will be set to automatically and repeatedly ramp on and off during an exercise session. After programming the stimulator (for CCFES and cNMES groups), the treating therapist will instruct and train the participants (and their caregivers if necessary), how to put on the components (i.e., electrodes, glove if applicable). The electrodes will be outlined on the skin and photographs of the electrodes correctly positioned will assist the subject in placing them correctly at home. An instruction manual will be reviewed with every participant, and each will be trained how to use their stimulator to complete their exercise sessions at home. Adherence to the home stimulation regimen will be collected with participant diaries and electronic data logging by the stimulator at every visit during the treatment period. From the stimulator's datalogger, the treating therapist will record the number of treatment sessions completed by the participant and the number of stimulated hand openings.

For all groups, treatment will last 12 weeks and consist of: (a) 10 sessions per week of self-administered exercises at home, and (b) 22 sessions of therapist-guided functional task practice in the lab (two per week except on weeks that include an assessment visit). Treatment regimens are:

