Blinded assessments will take place at baseline, mid-treatment(6 wk), end-of-treatment (12 wk), and at 3- and 6-months post-treatment. All assessments will be done with no electrical stimulation. Subjects will refrain from using their stimulators for 24 hours prior to their 6-week and 12-week assessments in order to avoid any transient carry over effects or muscle fatigue.

Box and Blocks Test (BBT): The primary endpoint is change in dexterity at 6-monthspost-treatment, as assessed by the BBT. The BBT is a measure of manual dexterity, which requires the subject to pick up one block at a time, move it over a partition, and release it in a target area as many times as

possible in 60 seconds. Participants will perform the test first with the unaffected hand, and then with the affected hand. The BBT is classified as an activity (ICF domain) measure by the Rehabilitation Measures Database and the Evidence-Based Review of Stroke Rehabilitation.

Upper Extremity Fugl-Meyer Assessment (UEFM). The UEFM is a measure of post-stroke upper limb motor impairment that takes into account synergy patterns, isolated strength, coordination, and hypertonia. Volitional movement of the upper limb (shoulder, elbow, forearm, wrist, and hand) is examined in and out of synergies. Each item is graded on a 3-point ordinal scale (0, cannot perform; 1, perform partially; and 2, perform fully) and summed to provide a maximum score of 66.

Action Research Arm Test, (ARAT): The ARAT is a measure of upper extremity functional ability. The ARAT is a 19-item test divided into four categories (grasp, grip, pinch, and gross movement), with 16 of the 19 ARAT items measuring distal regions of the arm, making it an ideal and sensitive measure for this distally based intervention.

Stroke Upper Limb Capacity Scale (SULCS). The SULCS is a 10-item test in which stroke patients are rated using a 2-point ordinal scale on their performance of upper limb tasks ranging from reaching forward to manipulating coins. It is a valid and reliable measure of upper limb capacity that is suitable for a wide range of patients including those with poor hand-related upper limb capacity.

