The primary analysis was based on a modified intention-to-treat (ITT) sample, which included participants in the group to which they were assigned who completed the treatment phase of the study. For all measures, changes from baseline were modeled using a linear mixed effects modeling approach, which accounts for missing values using maximum likelihood estimation. The linear mixed effects model using the restricted maximum likelihood (REML) estimator was employed, along with the Satterthwaite approximation to estimate the denominator degrees of freedom. While REML assumes normality of the random effects and residuals, it is generally more robust to violations of this assumption than traditional maximum likelihood, particularly in the estimation of fixed effects. The model included a random intercept to account for individual variability, and we specified a compound symmetry covariance structure to model the within-subject correlations. Least squares mean estimates were calculated after fitting each model for each group at each timepoint and were used to quantify within-group changes from baseline and between-group differences in change from baseline to 6 mos post-treatment. Statistical significance was set at $p < 0.05$. No adjustments were made for multiple comparisons in order to maintain a balance between Type I and Type II error rates. This balanced approach to error control was prioritized rather than strictly minimizing Type I error at the expense of statistical power and increasing the risk of overlooking meaningful effects. Pair-wise Chi-square tests were used to compare responder rates between groups.

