Exploratory subgroup analyses were performed using mixed effects models to test whether covariates (e.g., site, months since stroke, dose received, sex) moderated the change in BBT, UEFM, and ARAT scores across groups. A pre-planned analysis of only those participants with moderate hand weakness at baseline was conducted based on the prior study showing participants with moderate weakness achieved greater gains on the BBT than participants with severe hand weakness. Two pre-planned sensitivity analyses of the motor recovery outcomes were done. The first included all participants who were randomized to a treatment group regardless of the amount of treatment received. The second included only participants who received no other upper limb physical therapies during the treatment period and completed at least 80% of the planned treatment, i.e., at least 18 out of 22 FTP visits and at least 8 out of 10 home exercise sessions per week on average.

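### The primary modified-ITT set keeps only participants who completed the 12-week treatment phase, so the 6-month contrasts are not guaranteed the protection of randomisation; the planned all-randomised analysis should lead.

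*Combined protocol and SAP*

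**What the plan says.** The protocol (Methods and Procedures) describes an assessor-blinded trial with a target of 132 patients randomised to CCFES, cNMES or TOT. On treatment it states "For all groups, treatment will last 12 weeks and consist of" home and lab sessions. Assessments are at baseline, 6 weeks, 12 weeks, and 3 and 6 months post-treatment, and all subjects are to be followed to the last of these. Under Outcome Measures: "The primary endpoint is change in dexterity at 6-monthspost-treatment, as assessed by the BBT".

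The Statistical Analysis Plan section then says:

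- **Primary set:** it is labelled modified ITT, and its definition reads "which included participants in the group to which they were assigned who completed the treatment phase of the study".
- **Missing data:** changes from baseline go into a linear mixed model, "which accounts for missing values using maximum likelihood estimation".
- **Responders:** "Pair-wise Chi-square tests were used to compare responder rates between groups". Neither the analysis set nor the handling of missing scores is given for this test.
- **Sensitivity analyses:** there are two, both described as pre-planned and both for the motor recovery outcomes. "The first included all participants who were randomized to a treatment group regardless of the amount of treatment received". The second is narrower than the primary set: no other upper limb therapy, and "at least 18 out of 22 FTP visits and at least 8 out of 10 home exercise sessions per week on average".

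Completion of the treatment phase is not defined. It could mean reaching week 12, attending the 12-week assessment, or attending a minimum number of sessions. The separate 80% set suggests that it is not an adherence threshold.

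**The concern.** Randomisation makes the arms comparable as randomised. Once membership of the analysis set depends on something that happens during treatment, that comparability is no longer assured, and keeping people in their assigned arm does not restore it.

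The arms also give different reasons to stop. The Potential Risks section calls electrode-related skin redness and stimulation discomfort common, and these apply to CCFES and cNMES only. CCFES adds a sensor glove and cued exercise, cNMES runs automatically, and TOT has no stimulator. Participants know what they are receiving.

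The set also works against the chosen model. Someone who stops between week 6 and week 12 already has a week-6 change score, which a likelihood-based mixed model could use. The completer rule discards it.

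At stake is the lead estimate for both aims: a superiority claim for CCFES would rest on a subset formed after randomisation.

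**Working it through.** No figure in the documents can be reproduced here. They give the target of 132 but no effect size, standard deviation, power or dropout rate. Every magnitude below rests on assumed inputs.

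**1. Shift from restricting to completers.** In one arm let p be the non-completion proportion and d the mean gain of completers minus that of non-completers. The all-randomised mean is (completers' mean) - p × d, so restricting to completers raises that arm's mean by p × d. For CCFES (1) against a comparator (0):

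completers-only difference minus all-randomised difference = p1 × d1 - p0 × d0

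With an assumed common d of 6 blocks:

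- 20% versus 10%: 0.20 × 6 - 0.10 × 6 = **+0.6 block** (towards CCFES)
- 10% versus 25%: 0.10 × 6 - 0.25 × 6 = **-0.9 block** (against CCFES)
- equal p and equal d: **0**

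Equal rates alone are not enough. If p1 = p0 but d1 and d0 differ, the shift is p × (d1 - d0).

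**2. Type I error under a true null.** Assumptions: 44 randomised per arm (132/3, taking 1:1:1 allocation, which is not stated), two-sided 0.05, and a latent tendency to complete that has correlation rho with the standardised 6-month change. The completers' mean then shifts by rho × phi(z_p)/(1 - p) SD, where phi is the standard normal density and z_p the p-quantile.

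One case in full, with 20% non-completion in each arm, outcome-related in one arm only, and rho = 0.5:

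- shift = 0.5 × 0.280/0.80 = 0.175 SD
- SE = sqrt(2/35.2) = 0.238, so shift/SE = 0.734
- type I error = Φ(-1.96 + 0.734) + Φ(-1.96 - 0.734) = 0.114

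| Non-completion | Mechanism | Shift in SD (rho 0.2 to 0.5) | Type I error |
|---|---|---|---|
| 20% vs 20% | same in both arms | 0 | 0.050 |
| 20% vs 10% | same in both arms | 0.03 to 0.08 | 0.052 to 0.063 |
| 20% vs 20% | outcome-related in one arm only | 0.07 to 0.18 | 0.060 to 0.114 |
| 25% vs 5% | outcome-related in the 25% arm only | 0.09 to 0.21 | 0.065 to 0.149 |

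For scale, 44 per arm detects about 0.60 SD with 80% power.

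**3. Precision.** Assume 15% are excluded (0.15 × 132, about 20 participants). The SE factor relative to full data is 1/sqrt(0.85) = 1.085.

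- If the non-completers have 6-month scores, including them brings the factor back to 1.
- If they have week-6 data only, with correlation r between week-6 and 6-month change and the covariance treated as known, the variance factor is r² + (1 - r²)/0.85. At r = 0.5 this is 0.25 + 0.882 = 1.132, an SE factor of 1.064. At r = 0.7 it is 0.49 + 0.60 = 1.09, an SE factor of 1.044. The recovery is 1.085 - 1.064 = 0.021 to 1.085 - 1.044 = 0.041, about 2 to 4 percentage points.
- Someone who stops before week 6 and never returns has no change score and adds nothing to this model.

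**The case against.** The best defence is that the safeguard is already in the plan. Participants are analysed as assigned, and a pre-planned analysis of everyone randomised covers the motor recovery outcomes. If the two sets disagreed, a reader would see it. On this view the dispute is only about which planned analysis is called primary, and the effect may be small: at 20% versus 10% with a common mechanism, type I error is no more than 0.063 in the cases above.

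Much of that stands. A reader might infer that the plan has no intention-to-treat analysis, and that would be wrong. A reader might also infer that the primary result is biased; the documents do not show that, and the larger error rates need outcome-related dropout in one arm only. The defence fails on two points. The label decides which estimate carries the superiority claim, and no all-randomised analysis is stated for the patient-reported outcomes that Aim 1 includes.

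Two further inferences are tempting and unsupported. One is that the chi-square comparison uses the completers set and drops anyone without a 6-month score. The SAP states neither, and counting missing scores as non-response fits its text equally well. The other is that the past tense means the set was chosen after the data were seen. The documents do not say when it was defined.

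**Conclusion.** The point holds for the definition of the primary set. It is a completers set under an ITT label, so protection by randomisation is not guaranteed for the primary endpoint in either aim, and the mixed model's treatment of missing values cannot repair an exclusion made before the model is fitted.

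The size is unknown. Under the assumed inputs the shift is zero to under one block in either direction, and the loss of precision is about 8.5% in SE at 15% exclusion. The shift depends on how many participants stop, whether that differs by arm, and how it relates to outcome; the documents give none of these. An all-randomised analysis removes the bias due to the exclusion only if non-completers' outcomes are collected, or are missing at random given the observed data. This should be corrected because it concerns the lead analysis and the remedy is already in the plan.

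**What to change.** Swap the roles of the two analyses.

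- **Primary:** all randomised participants in their assigned arm, with all available visits in the mixed model, for all outcomes including the patient-reported ones.
- **Sensitivity:** the current completers set, with completion of the treatment phase defined and the number excluded reported by arm.
- **Responders:** run the comparison on the same all-randomised set and state how missing 6-month scores are handled. Imputing them from the other visits is a reasonable choice.
- **If the analysis is already done:** lead with the all-randomised estimate and disclose the change.

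The swap itself is a wording change in the SAP, since the all-randomised analysis is already planned for the motor outcomes. Extending it to the remaining outcomes and imputing responder status are small added analyses. The visit schedule is untouched. The downside is a possibly diluted point estimate and slightly more analysis work.

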Research Hypothesis: At 6 mo post-treatment, improvements in hand function will be significantly greater after CCFES than TOT, and a greater proportion of participants will achieve clinically significant improvements after CCFES than TOT.

Methods and Procedures

This is a 4-site, assessor-blinded Phase II randomized controlled trial to determine whether CCFES is superior to cNMES or TOT in improving hand function in patients with upper extremity hemiplegia who are between 6 and 24 months past their stroke. A target of 132 patients will be randomized to Contralaterally Controlled Functional Electrical Stimulation (CCFES), Cyclic Neuromuscular Electrical Stimulation (cNMES), or Task Oriented Training (TOT). Stratification factors include age, severity of hand impairment, months post-stroke, and treatment site.

All groups will receive 12 weeks of upper limb rehabilitation treatment consisting of a home regimen and functional task practice in the lab. Treatment will include: 1) therapist-administered 90-min sessions of hand task practice twice a week in the lab, and 2) self-administered sessions lasting approximately 1 hour per session 10 times a week at home.

- CCFES group: 90-min 2x/week CCFES therapy with therapist + 10x/week CCFES hand opening exercise self-administered at home.
- cNMES group: 90-min 2x/week therapy with therapist + 10x/week cNMES hand opening exercise self-administered at home.
- TOT group: 90-min 2x/week therapy with therapist + 10x/week home exercise program self-administered at home.

All subjects will be followed for 6 months post-treatment. Blinded assessments will take place at baseline, mid-treatment (6 wk), end-of-treatment (12 wk), and at 3- and 6-months post-treatment.

Baseline characteristics will be collected, including demographic (e.g., sex, age, race, pre-morbid hand dominance), stroke-related (e.g., time post-stroke, hemorrhagic or ischemic, cortical or subcortical, right or left, Stroke Impact Scale score), and neurologic data (e.g., side of hemiparesis, cognition,

depression, neglect, visual deficits, aphasia), as well as co-morbidities, and medications. The balance of these between the three groups and their effect on the outcomes will be evaluated.

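### The SAP does not state that the primary mixed model adjusts for baseline BBT or any of the four stratification factors, at a precision cost the documents do not determine

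*Combined protocol and SAP*

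**What the plan says.** Under Outcome Measures, the protocol defines the endpoint: "The primary endpoint is change in dexterity at 6-monthspost-treatment, as assessed by the BBT".

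The Statistical Analysis Plan gives change from baseline as the response: "For all measures, changes from baseline were modeled using a linear mixed effects modeling approach". It then gives the covariance: "The model included a random intercept to account for individual variability, and we specified a compound symmetry covariance structure". The fixed effects have to be inferred from one sentence: "Least squares mean estimates were calculated after fitting each model for each group at each timepoint". That implies group, visit and their interaction. There is no full list, and no statement that other terms were left out.

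On randomisation, Methods and Procedures says: "Stratification factors include age, severity of hand impairment, months post-stroke, and treatment site". Two of these factors return in the SAP, but only as possible moderators: "Exploratory subgroup analyses were performed using mixed effects models to test whether covariates (e.g., site, months since stroke, dose received, sex) moderated the change". Methods and Procedures also says of the baseline characteristics: "The balance of these between the three groups and their effect on the outcomes will be evaluated". That sentence is not tied to the primary model.

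On severity, the SAP says: "A pre-planned analysis of only those participants with moderate hand weakness at baseline was conducted". Its reason is a prior study in which participants with moderate weakness gained more on the BBT than those with severe weakness.

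**The concern.** A trial that stratifies its randomisation would normally carry the stratifiers into the primary model. If a stratifier predicts the outcome and is then ignored, the balance built in by design makes the estimate more precise than the model's SE shows. Baseline score is a separate matter: a change score subtracts it with a fixed coefficient of one, whereas a covariate lets the data choose the coefficient.

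Three features make this relevant here. The cited prior study suggests that severity predicts BBT gain. The primary set is limited to participants who completed the treatment phase, which may weaken the balance that stratification gave. The SAP also declines multiplicity adjustment in order to protect power, so giving up power through omitted covariates runs against its own reasoning.

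Separately, an analysis of moderate participants alone gives one stratum's estimate. Without the severe stratum's estimate and a test of the difference, it cannot show that the treatment effect depends on severity.

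**Working it through.** **Inputs from the documents.** Target of 132 randomised to three groups, 4 sites, and follow-up assessments at 6 and 12 weeks and at 3 and 6 months post-treatment (Methods and Procedures); significance level 0.05 (SAP). The text gives no effect size, SD, power, dropout rate or baseline-to-follow-up correlation with the 132, so that figure cannot be reproduced.

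**Assumed.** 44 per arm (132/3), no dropout, two-sided testing. ρ is the correlation of baseline with 6-month BBT, k the ratio of follow-up SD to baseline SD, and R² the share of change-score variance explained by the stratifiers.

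**Step 1: reference difference.** In SDs of change, 80% power at 44 per arm needs d = (1.960 + 0.842) × √(2/44) = 2.802 × 0.2132 = 0.597.

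**Step 2: stratifiers omitted, fully balanced by design.** The true SE is √(1 − R²) times the unadjusted model SE. Hence:
- SE overstatement = 1/√(1 − R²)
- type I error = 2[1 − Φ(1.960/√(1 − R²))]
- unadjusted power = Φ(0.842/√(1 − R²))
- adjusted power = Φ(2.802/√(1 − R²) − 1.960)

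| R² | SE too wide by | Type I error | Power unadjusted | Power adjusted |
|---|---|---|---|---|
| 0 | 0% | 0.050 | 80% | 80% |
| 0.1 | 5% | 0.039 | 81% | 84% |
| 0.2 | 12% | 0.028 | 83% | 88% |
| 0.3 | 20% | 0.019 | 84% | 92% |

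**Step 3: simulation check.** 6,000 runs, blocks of three within severity × site, a single 6-month endpoint, R² = 0.2. The unadjusted estimate had empirical SD 0.190 against a mean model SE of 0.213. Type I error was 0.027 unadjusted and 0.046 adjusted; power at d = 0.6 was 82% and 88%. With unstratified allocation and the same R², unadjusted type I error was 0.050. The conservatism therefore comes from stratifying and then ignoring the strata, not from omitting a covariate as such.

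**Step 4: baseline omitted.** With baseline SD set to 1, the variance of change is 1 + k² − 2ρk and the baseline-adjusted variance is k²(1 − ρ²). The difference is (1 − ρk)², so the gain vanishes when ρk = 1. With the unadjusted analysis set at 80% power, adjusted power is:
- k = 1: 90% at ρ = 0.5, 86% at 0.7, 84% at 0.8, 82% at 0.9. At k = 1 the variance ratio is (1 + ρ)/2, so the N giving the same precision as 132 unadjusted is 99, 112, 119 and 125.
- k = 1.3: 80.4% at ρ = 0.7, 80.1% at 0.8, 83% at 0.9, 90% at 0.95.

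The range is 0 to 10 points.

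**Step 5: an opposing effect.** Compound symmetry pools the variance over visits. If the SD of change rose as 0.8, 0.9, 1.0, 1.1 (assumed), the pooled SD is √(3.66/4) = 0.957. The 6-month SE would then be 0.957/1.1 = 0.87 of its true value, and type I error about 0.088.

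**The case against.** The strongest reply is that the SAP is silent rather than wrong. Since even group and visit must be inferred, a reader might infer that the adjusting terms were definitely excluded; the text supports only that their inclusion is not stated. This stands, and the point is limited to that. A primary model without a stated list of fixed effects needs completing either way.

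A reader might also infer that the plan's error bars are conservative overall. The documents do not support that. The result in Step 2 needs prognostic stratifiers and effective balance, and neither the factor levels nor the allocation method is given. With two levels assumed for each of three factors, 4 × 2 × 2 × 2 = 32 cells hold about 132/32 ≈ 4 participants each across three arms, so balance could be partial. Step 5 shows that compound symmetry can push the SE the other way.

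Nor does it follow that chance imbalance goes uncorrected. Stratification limits it on the four factors, less surely among completers. A change score leaves only (ρk − 1) times the baseline imbalance, for example −0.3 times at ρ = 0.7 and k = 1.

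It is fair, too, that the prior study's finding comes without a size and may not have held in every arm. If it carries over to baseline BBT, participants who start higher gain more. That requires ρk > 1, so the k = 1 figures would not apply and the gain could be near zero.

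Finally, the moderate-only analysis is additional. Nothing in the SAP drops severe participants from the primary analysis. The list of moderators is open-ended, so a severity test is not ruled out; it is simply not named.

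**Conclusion.** The concern holds as one of incomplete specification and avoidable loss of precision. The SAP does not state that the primary model includes baseline BBT or any stratifier, and the promise to evaluate the effect of baseline characteristics does not supply those terms.

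The size cannot be taken from the documents. For stratifiers explaining 10–20% of change-score variance and balanced by design, the loss is roughly 3 to 6 power points, the upper figure from the simulation. For baseline it is 0 to 10 points depending on ρ and k. These losses are alternative calculations and should not be added, because baseline BBT and severity overlap. If the stratifiers explain nothing, omitting them costs nothing. Leaving out baseline does not by itself invalidate the SE, and the omission of these terms is not a source of type I inflation.

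The moderate-only analysis is legitimate as planned, but cannot alone support a claim of effect modification.

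**What to change.** State the fixed effects in full for each mixed model: group, visit, group-by-visit, baseline value of the measure, baseline-by-visit, site, severity stratum, age and months post-stroke. The added terms cost about 10 degrees of freedom: baseline 1, baseline-by-visit 3 (four follow-up visits), site 3 (four sites), severity 1 (two levels assumed), age 1, months post-stroke 1. All these variables are already collected. If any is to be left out, give the reason.

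The SAP is written in the past tense. If the unadjusted model was already pre-specified and run, keep it as primary and report the adjusted model as a labelled sensitivity analysis.

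Keep the moderate-only analysis. Beside it, fit a treatment-by-severity interaction at 6 months in the full sample, and report the treatment difference in both strata, the interaction, and confidence intervals for all three. The interaction will be imprecise: with two equal strata (assumed), each stratum's variance is twice that of the overall contrast, their difference has four times, and its SE is doubled. The cost is a few sentences in the SAP and a few model terms, with no new data.

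### Compound symmetry gives all four post-baseline visits one variance, so the standard error of the primary 6-month contrast is right only if the 6-month variance equals the visit average

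*Combined protocol and SAP*

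**What the plan says.** Under Statistical Analysis Plan, the response is change from baseline ("changes from baseline were modeled using a linear mixed effects modeling approach"), fitted by REML "along with the Satterthwaite approximation to estimate the denominator degrees of freedom". The covariance is given as: "The model included a random intercept to account for individual variability, and we specified a compound symmetry covariance structure". Least squares means are obtained for each group at each timepoint and used for "between-group differences in change from baseline to 6 mos post-treatment".

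Under Outcome Measures, "The primary endpoint is change in dexterity at 6-monthspost-treatment, as assessed by the BBT". Methods and Procedures gives the schedule: "Blinded assessments will take place at baseline, mid-treatment (6 wk), end-of-treatment (12 wk), and at 3- and 6-months post-treatment". That makes four post-baseline visits, of which the last carries the primary contrast.

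The plan names no visit-specific variance, robust standard error, check of the covariance assumption or fallback structure. Its two pre-planned sensitivity analyses change which participants are included, not the covariance model. On distributional assumptions it says of REML that "it is generally more robust to violations of this assumption than traditional maximum likelihood, particularly in the estimation of fixed effects".

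**The concern.** A random intercept with independent residuals already implies compound symmetry (with a non-negative correlation). Naming both adds no flexibility: the model has one total variance and one correlation for every visit.

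That matters because the primary contrast sits at a single visit. If the spread of Box and Blocks Test (BBT) change differs between visits, the model takes its standard error from the pooled variance and not from the 6-month variance. The Satterthwaite method adjusts the degrees of freedom; it does not repair a variance estimated for the wrong quantity. At stake are the width of the primary confidence interval and the true level of a test declared at 0.05. The plan applies the same model to all measures and makes no multiplicity adjustment, so nothing elsewhere would offset an inflated error rate.

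**Working it through.** **Inputs from the documents.** Change from baseline at 6 weeks, 12 weeks, 3 months and 6 months post-treatment; random intercept with compound symmetry; REML with Satterthwaite degrees of freedom; contrast at 6 months; significance level 0.05; target of 132 randomized in three groups.

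**Assumptions, because the documents are silent.** Two-sided test; 1:1:1 allocation (132/3 = 44 per arm); separate mean for each group at each visit; equal variances across arms; SD of BBT change at each visit (patterns below); complete data for the formula.

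**Formula.** Let v1 to v4 be the variances of change at the four visits. With balanced data:

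- model SE² = mean(v1, …, v4) × (1/n1 + 1/n2)
- true SE² = v4 × (1/n1 + 1/n2)
- R = model SE / true SE = √(mean(v) / v4)
- actual type I error ≈ 2 × [1 − Φ(1.96 × R)]

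The sample sizes cancel in R.

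**Reproducing the nominal level.** With constant SD, R = 1 and the formula returns 0.050. A simulation of 3 × 44 participants (20,000 trials, REML under compound symmetry, Satterthwaite degrees of freedom) gave 0.049.

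**Assumed SDs of change (blocks), in visit order:**

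| SDs | Mean variance | 6-month variance | R | Type I error |
|---|---|---|---|---|
| 5, 6, 6, 6 | (25+36+36+36)/4 = 33.25 | 36 | 0.961 | 0.060 |
| 4, 5, 5.5, 6 | (16+25+30.25+36)/4 = 26.81 | 36 | 0.863 | 0.091 |
| 4, 5.5, 6.5, 7.5 | (16+30.25+42.25+56.25)/4 = 36.19 | 56.25 | 0.802 | 0.116 |
| 6.5, 6, 5.5, 5 | (42.25+36+30.25+25)/4 = 33.38 | 25 | 1.155 | 0.024 |

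**Scale-free check.** This uses the ratio of the 6-month SD to the 6-week SD, linear across visits, with the same simulation set-up:

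| SD ratio | By formula | Simulated, compound symmetry | Simulated, 6-month variance |
|---|---|---|---|
| 0.8 | 0.027 | 0.026 | 0.050 |
| 1.1 | 0.061 | 0.063 | 0.051 |
| 1.25 | 0.077 | 0.079 | 0.051 |
| 1.5 | 0.099 | 0.096 | 0.051 |
| 2.0 | 0.130 | 0.130 | 0.051 |

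Using the 6-month visit's own variance, as an unstructured covariance does with complete data, kept the error between 0.049 and 0.051 in every pattern tried.

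**Variance or correlation?** With constant SD and a correlation that decays between visits, simulated type I error was 0.050 with complete data. It was 0.045 with assumed dropout (10% missing at 3 months, 15% at 6 months, completely at random; 3,000 trials). Unequal variance drives the error, not the shape of the correlation.

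**REML sentence.** With complete balanced data, REML and maximum likelihood give the same fixed-effect estimates; a check on simulated skewed data found a maximum difference of 3e-14. REML reduces bias in the variance components.

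**The case against.** The strongest reply is that nothing in the documents shows the variances to be unequal, or in which direction. Treatment ends at 12 weeks and two of the four visits fall after it, so the spread may level off; with 5, 6, 6, 6 the error is only about 6%. If spread narrows after treatment, the test is conservative. This stands. A reader might infer that the primary p-value is anti-conservative, on the ground that change scores spread out with time. Two features make this plausible: eligibility spans hand Fugl-Meyer scores of 1 to 11 out of 14, and the plan cites a prior study in which moderately weak participants gained more on the BBT than severely weak ones. Neither is a visit SD, and neither settles the direction.

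Three further inferences also fail:

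- **That the error is 5% only with constant SDs.** The condition is that the 6-month variance equals the visit average. SDs of 5, 6.5, 6, 5.87 vary, yet average (25+42.25+36+34.46)/4 = 34.43 against 34.46 at 6 months, which gives 5%.
- **That using other visits to inform missing 6-month values inflates the error.** The dropout check with constant SD gave 0.045.
- **That figures for a model of raw scores with baseline as a response apply.** The plan says that changes were modeled.

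It is also fair that naming the structure twice is loose wording that changes no result, and that removing the REML sentence alters no estimate or test.

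**Conclusion.** The point holds in a limited form. The stated covariance ties the standard error of the primary 6-month contrast to the average visit variance, and nothing in the plan checks or relaxes this. The resulting test can be liberal or conservative. Under the four assumed SD patterns the two-sided type I error runs from about 2.4% to about 12%, and a visit-specific variance restores about 5%. Those figures rest on assumed SDs, complete data, two-sided testing and equal variances across arms. The true direction and size in this trial cannot be determined from the documents.

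This is an inexpensive improvement to the primary analysis, not evidence that its result is wrong. The REML sentence is a minor wording matter: it should not be relied on as protection against non-normality.

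**What to change.** Specify an unstructured covariance over the four post-baseline visits, with no separate random intercept. If it does not converge, fall back to heterogeneous Toeplitz and then to heterogeneous compound symmetry, with that order written down. Report the SD of change at each visit, so that a reader can see whether pooling mattered. Drop or reword the REML sentence.

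The SAP is written in the past tense. If the analysis is already complete, keep the compound symmetry result as the stated primary analysis and report the unstructured model next to it as a labelled sensitivity analysis. Replacing the primary model once results are known would be a post hoc change.

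The cost is 10 covariance parameters (4 variances and 6 covariances) in place of 2, hence a few degrees of freedom, and possible non-convergence, which the fallback order covers. This defect does not require a different degrees-of-freedom method, or a permutation or bootstrap test.
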